Document Title: Methods Summary (for ClinicalTrials.gov): Subcutaneous Tissue Closure Techniques in Elective Cesarean Delivery

Document Date (Last Updated): 28 February 2026

Study Design and Setting

This was a single-center, prospective, parallel-group interventional study conducted in the Department of Obstetrics and Gynecology, Dursun Odabaşı Medical Center, Van Yüzüncü Yıl University, between 30 March 2022 and 20 October 2022. The study compared three predefined subcutaneous tissue closure strategies during elective cesarean delivery.

Participants

Adults scheduled for elective cesarean delivery were screened for eligibility. Written informed consent was obtained prior to participation.

Inclusion Criteria

- Age 18 years or older
- Undergoing elective cesarean delivery
- Subcutaneous adipose tissue thickness ≥ 2 cm
- Provision of written informed consent

Exclusion Criteria

- Conditions associated with impaired wound healing (e.g., diabetes mellitus, autoimmune disease)
- Chorioamnionitis, premature rupture of membranes, or other active infection
- Current systemic steroid use
- Refusal to participate

Surgical Technique and Interventions

All cesarean deliveries were performed via Pfannenstiel incision. The intervention was the method of subcutaneous adipose tissue management performed immediately prior to routine skin closure. The three study groups were:

- Group 1 (No subcutaneous suturing): no approximation of the subcutaneous adipose tissue prior to skin closure.
- Group 2 (Interrupted closure): approximation using three interrupted subcutaneous sutures placed along the incision prior to skin closure.
- Group 3 (Continuous non-locking closure): approximation using a single-layer continuous, non-locking running subcutaneous suture along the incision prior to skin closure.

Allocation

Participants were assigned in a 1:1:1 ratio (n = 100 per group) using a sequential repeating order based on the order of surgery (non-randomized allocation).

Data Collection and Variables

Demographic and obstetric variables were recorded at baseline. Operative variables included:

- Total operative duration (minutes)
- Subcutaneous tissue length (cm)
- If present, size of intraoperative subcutaneous fluid collection (cm)

Postoperative Assessments and Outcomes

Participants were followed through postoperative day 10.

On postoperative day 10, wound outcomes were assessed using:

1. Standardized clinical incision examination for findings consistent with wound infection (e.g., discharge, dehiscence, erythema, warmth).
2. Incision-site ultrasonography to evaluate wound-related findings, including subcutaneous fluid collection and other complications (e.g., abscess, hematoma, cavity formation).

Both assessments were performed using a predefined protocol; participants were blinded to group allocation.

Statistical Analysis

Analyses were performed using SPSS version 23.0 (IBM Corp., Armonk, NY, USA). Continuous variables were summarized as mean \pm standard deviation or median (interquartile range), and categorical variables as number (percentage). Normality was assessed using the Kolmogorov–Smirnov test. Between-group comparisons were performed using the Kruskal–Wallis test for continuous variables and Pearson chi-square test for categorical variables. Within-group comparisons across time points were evaluated using the Wilcoxon signed-rank test (two time points) or the Friedman test (three time points). Post-hoc pairwise comparisons were adjusted using Bonferroni correction where applicable. A two-sided p-value < 0.05 was considered statistically significant.

Ethics

Ethics approval was obtained from the Van Yüzüncü Yıl University Academic Ethics Committee on 30 March 2022 (Decision No: 07). All participants provided written informed consent.

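### Allocation by a fixed repeating order tied to order of surgery lets anyone who knows the order foresee the next group; no concealment is described and the unadjusted tests do not address the resulting risk of selection bias

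*Combined protocol and SAP*

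**What the plan says.** The Allocation section gives the group sizes, "Participants were assigned in a 1:1:1 ratio (n = 100 per group"), and the method: "using a sequential repeating order based on the order of surgery (non-randomized allocation"). The design section does not claim randomisation: "This was a single-center, prospective, parallel-group interventional study".

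Four other statements bear on the point.

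- Recruitment (Participants): "Adults scheduled for elective cesarean delivery were screened for eligibility". The operations were therefore planned and their order could be arranged.
- Consent (Participants): "Written informed consent was obtained prior to participation". Its timing relative to knowledge of the next group is not given.
- Entry (Inclusion Criteria): "Subcutaneous adipose tissue thickness ≥ 2 cm". Who measured this, how, and whether before the group was known are not stated.
- Blinding (Postoperative Assessments and Outcomes): "participants were blinded to group allocation". No blinding is stated for those who recruited, listed or operated.

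The Statistical Analysis section compares groups with Kruskal–Wallis and Pearson chi-square tests, Bonferroni-adjusted post hoc where applicable. It includes no adjustment for baseline factors.

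**The concern.** If the sequence repeats, a person who knows the last assignment and the order knows the next one. That matters here for two reasons. The sequence follows order of surgery in elective cases, so moving a woman on the list can change her group. Entry also turns on a measurement, so including or leaving out a borderline woman changes the group of every woman after her. Either can happen without intent.

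If it did happen, the groups could differ in wound risk before the closure step. A difference in wound outcome could then be spurious, and a real one could be hidden. Blinding the participants does not protect against this, because the route runs through staff. The planned tests compare raw group results, so they would carry any such imbalance straight into the p-values.

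**Working it through.** **1. The plan's own figure.** A three-step repeating order over 300 women gives 300 / 3 = 100 per group, which matches the stated group sizes. The plan gives no event rate, effect size or power, so there is no sample-size figure to reproduce.

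**2. Predictability.** This is the expected share of next assignments guessed correctly by someone who knows the past ones.

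| Method | Correct guesses |
|---|---|
| Fixed repeating order, once known | 100% |
| Simple 1:1:1 randomisation | 33.3% |
| Permuted blocks of 3, size known | (1/3 + 1/2 + 1) / 3 = 61.1% |
| Permuted blocks of 6, 9, 12, size known | 56.1%, 53.2%, 51.2% |

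The literal order of the three groups is not stated, but any fixed repeating order is equally predictable. Random block sizes should be harder to guess than known fixed ones; no figure was computed for them.

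**3. What steering could do to the planned tests.** The inputs from the plan are n = 100 per group, a two-sided 0.05 level, and a three-group Pearson chi-square with Bonferroni-adjusted pairs. Everything else is assumed: wound-event risk of 20% in high-risk and 5% in low-risk women, and no true effect of closure technique.

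- Group with 50% high-risk women: 0.50 × 20% + 0.50 × 5% = 12.5%.
- Group with 30% high-risk women: 0.30 × 20% + 0.70 × 5% = 9.5%.
- Third group midway (40% high-risk): 11.0%.
- Spurious difference between the extreme groups: D = 12.5% − 9.5% = 3.0 points. A 30-point gap in the high-risk share would give 0.30 × 15 = 4.5 points.

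Three-group chi-square (2 degrees of freedom): non-centrality = n × 2 × (D/2)² / [p(1 − p)], with p = 0.11 and p(1 − p) = 0.0979.

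- D = 0.03: 100 × 2 × 0.015² / 0.0979 = 0.46, rejection about 8.6%.
- D = 0.045: 100 × 2 × 0.0225² / 0.0979 = 1.03, rejection about 13.6%.

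Pairwise test of the two extreme groups: standard error = √(2 × 0.0979 / 100) = 0.0442, so D / SE = 0.68 and 1.02. Bonferroni over three pairs uses 0.05 / 3 = 1.7%.

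| Spurious difference | Three-group chi-square | Bonferroni pair | Single pair at 0.05, uncorrected |
|---|---|---|---|
| 0 | 5.0% | 1.7% | 5.0% |
| 3.0 points | 8.6% | 4.4% | 10.4% |
| 4.5 points | 13.6% | 8.5% | 17.4% |

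The second and third columns correspond to the stated analysis. The last is shown only for contrast.

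**The case against.** The strongest reply is that the plan hides nothing. It calls the allocation non-randomised and never uses the word randomised for the design, so this is a declared choice and not a contradiction. That stands. But the label does not tell a reader whether staff could foresee and influence assignment, and the plan neither checks for this nor adjusts for it.

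A second reply is that nothing shows steering took place. That stands too. A reader might infer that each group was known with certainty before a woman was listed, consented or judged eligible. The documents do not support this. They do not say who held the sequence, who set the list, or when thickness and consent were settled relative to it. If consent and screening were complete before the operating order was fixed, the group was not yet known at that point.

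A reader might also infer that the rotation locked each group to a fixed place on the daily list. The pace argues against it. From 30 March to 20 October 2022 there are 147 weekdays, so 300 / 147 is about 2.0 women per weekday. At a constant two per day, a three-group rotation balances first and second places exactly (50 of each per group). Of constant rates from one to four per day, only three would tie group to place. The documents also say nothing about list position tracking case complexity or surgeon seniority.

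Finally, the uncorrected pairwise rates (10.4% and 17.4%) should not be read as the inflation under this plan, because the stated analysis is a three-group test with Bonferroni-corrected pairs. Enrolment is also over, so the allocation of these women cannot be changed.

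**Conclusion.** The concern holds as a risk of selection bias. Allocation was foreseeable to anyone who knew the order, nothing in the documents describes concealment, and the planned comparisons are unadjusted. It does not hold as proof that bias occurred or as a charge of mislabelling.

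The size cannot be estimated from the documents. On the assumed risks and imbalance above, the planned three-group chi-square would be wrongly significant about 8.6% of the time with a 3-point spurious difference and 13.6% with 4.5 points, against 5%. A Bonferroni-corrected pair would be at about 4.4% and 8.5%, against 1.7%. These figures rest on the assumed 20% and 5% event risks, the assumed steering, a third group midway, and a normal approximation. With no steering there is no inflation from this source.

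**What to change.** **Any further enrolment.** Use a computer-generated 1:1:1 list in permuted blocks of random size, concealed until consent and a thickness of at least 2 cm have been recorded. This costs a list and a means of concealment, with no extra visits or patients. The downside is slightly less exact balance than a rotation gives.

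**The 300 women already enrolled.** The description of allocation must stay as it is, since it records what was done. Then:

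- State who knew the sequence, and when thickness and consent were settled relative to it.
- Check the theatre log for eligible women skipped or taken out of sequence, and report the count.
- Analyse each woman in the group her sequence position dictated.
- Report baseline balance, and add a comparison adjusted for the baseline demographic and obstetric variables already recorded. Include subcutaneous thickness if its value was recorded; the plan lists it as an entry criterion and does not name it among the collected variables.
- State conclusions as non-randomised comparisons.

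The cost is a log review, one added analysis and some wording. These steps limit and disclose the problem. They cannot remove bias from unrecorded factors, and analysis by sequence position does not undo a list order that was itself arranged.

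### Allocation followed a predictable, non-randomised order, yet no covariate-adjusted comparison, effect estimate or confidence interval is described, so any measured baseline imbalance would go uncorrected

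*Combined protocol and SAP*

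**What the plan says.** Three sections of the combined protocol and SAP bear on this point.

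- **Allocation.** Women were placed 1:1:1, 100 per group, by rotating through the groups in the order in which operations took place. The document itself calls this "non-randomized allocation". It describes no concealment of the next assignment.
- **Data Collection and Variables.** "Demographic and obstetric variables were recorded at baseline". The individual variables are not listed.
- **Statistical Analysis.** "Between-group comparisons were performed using the Kruskal–Wallis test for continuous variables and Pearson chi-square test for categorical variables". For pairs, "Post-hoc pairwise comparisons were adjusted using Bonferroni correction where applicable". The remaining tests (Wilcoxon signed-rank, Friedman) are within-group. Results are summarised per group as means, medians or percentages, and significance is judged at a two-sided 0.05.

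No regression, stratified, matched or propensity analysis is described. Nor is any between-group difference, ratio or confidence interval.

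**The concern.** An unadjusted test speaks to the effect of closure technique only if the groups are comparable in everything else that affects wound outcome. Randomisation would justify that assumption; a rotation that anyone in theatre can foresee does so less securely. Whoever knows the last case knows the next assignment, so enrolment or list order could be influenced. The usual partial safeguard is to adjust for recorded prognostic factors, and the plan describes none. The Bonferroni correction deals with multiple comparisons and does nothing about imbalance.

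A second gap stands whether or not the groups are balanced. With no interval for the difference between groups, a non-significant result at 100 per group could be read as showing no difference when sizeable differences remain possible.

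**Working it through.** The document gives no event rate, target difference, power or baseline distribution, so it has no figure of its own to reproduce. From the document come three groups, 100 women per group, a Pearson chi-square test and a two-sided 0.05. **Everything else below is assumed.**

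**1. Do the named tests use baseline data?** Set side by side, Allocation declares the comparison non-randomised, Data Collection and Variables says baseline data exist, and Statistical Analysis names only tests that take an outcome and a group label. Nothing links the baseline data to the outcome comparison.

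**2. How much apparent difference would an imbalance create?** Assume one binary prognostic factor, a 10% event risk without it, and no effect of closure. With odds ratio OR, the risk with the factor is p₁ = (OR × 0.10/0.90) / (1 + OR × 0.10/0.90). This gives 18.2%, 25.0% and 30.8% for OR 2, 3 and 4. If the factor's prevalence is 50% in one group and 30% in another, the spurious risk difference is (0.50 − 0.30) × (p₁ − 0.10):

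- OR 2: 0.20 × 0.082 = 1.6 points
- OR 3: 0.20 × 0.150 = 3.0 points
- OR 4: 0.20 × 0.208 = 4.2 points

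**3. What does that do to the test?** The simulation used 40,000 trials per scenario, 100 per group, the assumptions of step 2 and no treatment effect. The crude test is the three-group Pearson chi-square (2 df). The stratified test is Cochran–Mantel–Haenszel on the factor.

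| Prevalence across groups | Crude, OR 2 / 3 / 4 | Stratified |
|---|---|---|
| 40/40/40% | 5.0 / 5.1 / 4.8% | about 5% |
| 45/40/35% | 5.1 / 5.4 / 6.1% | about 5% |
| 50/40/30% | 5.9 / 7.5 / 9.6% | about 5% |
| 60/40/20% | 8.4 / 16.2 / 25.2% | about 5% |

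The stratified test recovers the nominal level because the factor is measured and used. It would not do so for an unmeasured one.

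**4. Is a 50/40/30% split plausible by chance?** At a common prevalence of 40%, the standard error of the difference between two groups of 100 is √(2 × 0.4 × 0.6 / 100) = 0.069. A 20-point gap is then 0.20/0.069 = 2.9 standard errors. The exact binomial probability of a gap of 20 points or more is about 0.5% per pair. A split that wide would mostly require interference with the order.

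**5. How wide is the missing interval?** The 95% half-width for a pairwise risk difference is 1.96 × √(2p(1 − p)/100):

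- p = 10%: 1.96 × √0.0018 = 0.083, or ±8.3 points
- p = 5%: 1.96 × √0.00095 = 0.060, or ±6.0 points

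**The case against.** A reader might infer that confounding is present and has biased the results. The documents do not support that. Allocation was by rotation, not by prognosis, surgeon's preference or patient's choice. If the order was kept, no systematic imbalance is expected and the crude tests hold their level, as the balanced row shows. The Exclusion Criteria also remove several strong influences on wound healing: diabetes, autoimmune disease, active infection, ruptured membranes and steroid use. All of this stands. What remains is that the order was foreseeable, that no concealment is described, and that age, obstetric history and the amount of subcutaneous tissue above the entry threshold can still vary.

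A reader might also quote a larger error rate. Take a factor carrying a 20% risk with it and 5% without, and a 50% v 30% split. A single uncorrected pairwise test then rejects in about 10.7% of null trials. But the plan uses a three-group test with Bonferroni-corrected pairs. Under the same risks and a 50/40/30% split, the overall test rejects in about 8.4% and the corrected pairwise test in about 4.1% (nominal 0.05/3 = 1.7%). The inflation is real under the assumption, but smaller.

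Three further objections hold and narrow the remedy:

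- Regression corrects only measured factors. It does not repair selection on unmeasured ones, or unblinded assessment, which is possible because blinding is stated for participants only.
- The per-group summaries would let a reader derive crude differences, so the missing intervals are a reporting gap and not a loss of information.
- Data were collected in 2022, so a regression chosen now adds analyst choice. That argues for placing it beside the described analysis and not in place of it.

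**Conclusion.** The point holds in a limited form. For a predictable allocation that the document calls non-randomised, no adjusted analysis and no between-group interval is described, although baseline data were recorded. A measured imbalance, if there was one, would go uncorrected.

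Its size is conditional. There is no inflation if the groups are balanced and little at 45/40/35%. The false-positive rate is about 6–10% at 50/40/30% and about 8–25% at 60/40/20%, for odds ratios of 2–4 and a 10% risk without the factor. All these prevalences, risks and odds ratios are assumptions, and so are the event rates behind the ±8.3 and ±6.0 points. The document does not show that an imbalance occurred, so the conclusion is that the analysis lacks a safeguard, not that its results are wrong. Severity: should-fix.

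**What to change.** - Show the recorded baseline variables by group.
- Keep the crude tests and add a covariate-adjusted between-group analysis beside them. For binary day-10 wound outcomes use logistic regression, Firth-penalised if events are few. For operative duration use linear regression with robust standard errors.
- Include group plus a short fixed set of pre-closure covariates chosen from those actually recorded, for example age, obstetric history, and subcutaneous thickness or BMI if recorded. The document lists neither BMI nor individual obstetric variables. Thickness appears only as an entry threshold, while the listed operative variable is a subcutaneous tissue length, so availability must be checked first.
- Report adjusted differences with 95% confidence intervals for all three pairs: risk differences for wound outcomes and minutes for duration.
- Do not adjust the wound models for operative duration or fluid collection, since both may follow from the closure.
- Label the adjusted analysis post hoc unless it was pre-planned. State that it corrects only measured factors and does not repair the lack of concealment or possible unblinded assessment.

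**Cost:** a few lines of analysis text and a few hours' work, with no new data collection provided suitable covariates were recorded. The downside is that the covariate set must stay small where events are rare, so adjustment may be thin for the least common outcomes.

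### No primary outcome is named and 0.05 applies to every outcome with no control across outcomes; the chance of at least one false positive is about 10% to 34%, depending on how many outcomes are tested

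*Combined protocol and SAP*

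**What the plan says.** Postoperative Assessments and Outcomes describes two assessments on postoperative day 10. The clinical examination looks for "findings consistent with wound infection (e.g., discharge, dehiscence, erythema, warmth"). The ultrasound covers "subcutaneous fluid collection and other complications (e.g., abscess, hematoma, cavity formation"). Both lists are given by example. No outcome is called primary or secondary, and there is no composite or order of importance. Allocation gives 100 women in each of three groups, with no sample-size reasoning that would point to a main outcome.

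Statistical Analysis sets out the tests by type of variable: "Between-group comparisons were performed using the Kruskal–Wallis test for continuous variables and Pearson chi-square test for categorical variables". One threshold covers all of them: "A two-sided p-value < 0.05 was considered statistically significant". The single statement on multiplicity is "Post-hoc pairwise comparisons were adjusted using Bonferroni correction where applicable". The document is headed as a methods summary for a trial registry, is written in the past tense, and carries a last-updated date of "28 February 2026".

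**The concern.** A 5% threshold limits the false-positive risk for one test. When several outcomes share it and none is set apart, the risk that at least one crosses the line by chance grows with their number, and whichever does so can be presented as the trial's positive result. Nothing in the document would show a reader whether that outcome was the intended one.

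The Bonferroni step does not help. It divides the error among the three group pairs inside one outcome and leaves the number of outcomes untouched.

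Timing adds to this. The study ran until 20 October 2022 and the document was last updated 1,227 days later, so it cannot by itself establish that an outcome was fixed before the data were seen.

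**Working it through.** **Inputs from the document.** Three groups of 100; two-sided 0.05 for every test; no correction across outcomes; two day-10 assessments; four clinical signs named (discharge, dehiscence, erythema, warmth); four ultrasound findings named (fluid collection, abscess, hematoma, cavity). The document gives no familywise error, power or event rate, so there is no figure of its own to reproduce.

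**Assumption.** The document does not say how many outcomes are tested. Three readings of k, the number of three-group tests, are taken.

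**Formula.** If no outcome differs between groups and the tests are independent, the chance of at least one p-value below 0.05 is 1 − 0.95^k.

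| Reading | k | Calculation | Chance of at least one false positive |
|---|---|---|---|
| One outcome per assessment | 2 | 1 − 0.9025 | 9.8% |
| One infection outcome plus four ultrasound findings | 5 | 1 − 0.7738 | 22.6% |
| All eight named findings separately | 8 | 1 − 0.6634 | 33.7% |

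**Effect of correlation.** Wound findings in the same woman will tend to occur together, which lowers these figures. Eight binary findings were simulated with 100 women per group, no true differences, a three-group chi-square test on each at 0.05, and 6,000 runs per setting. Event rates of 1% to 20% and the latent correlations are assumptions.

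- Correlation 0 to 0.5: about 30% to 34%.
- Correlation 0.8: about 24% to 26%.

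**Does the pairwise Bonferroni step change this?** No. The figures count significant three-group tests, one per outcome. Bonferroni acts on the pairs within an outcome, at 0.05/3 = 0.0167 per pair, and does not alter the 0.05 applied to the three-group test.

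**After the fix.** One named primary outcome tested at 0.05 has a false-positive risk of 5%. If all eight findings were kept as claims, Holm would start at 0.05/8 = 0.00625. Using that level for all eight (plain Bonferroni) gives 1 − (1 − 0.00625)^8 = 4.9% under independence, and 2.4% to 5.0% in the same simulations. Holm is never less powerful than plain Bonferroni and holds the error at or below 5% whatever the correlation, provided the individual p-values are valid.

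**The case against.** The strongest reply is that the plan never says each sign is tested. Discharge, dehiscence, erythema and warmth are examples of one construct, wound infection, and analysing them as one outcome is at least as natural as testing four. Abscess, hematoma and cavity are likewise examples under a general heading. This stands, and it is why the size is given as a range. It does not remove the problem: two outcomes with no stated priority already give nearly 10%.

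A reader might infer a figure of 40% by counting ten outcomes (1 − 0.95^10 = 40.1%). The documents do not support that count. The two additions, operative duration and size of fluid collection, appear under Data Collection and Variables as operative variables; the latter is intraoperative and recorded only if present. Even 34% is an upper reading, not a property of the plan.

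A second reply is that this is only a registry summary. The registry record or the protocol submitted for ethics approval may name a primary outcome, and neither is among the documents. This also stands: the defect shown is in this document and may be curable by citing another. For the same reason, a reader might infer that outcomes were picked after the results were known. A last-updated date does not show when outcomes were chosen, so the documents support only the weaker statement that they give no evidence of choice in advance.

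**Conclusion.** The point holds. The document names no primary outcome and uses 0.05 for every outcome with no control across them. The chance of at least one false positive is about 10% to 34%, according to whether two, five or eight outcomes are tested. Those figures assume independence and no true differences. For eight findings the figure falls to about 24% to 26% at latent correlation 0.8, under assumed event rates.

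A reader might also infer that the Bonferroni step on pairs is misplaced, since with three groups a three-group test at 0.05 followed by unadjusted pairs already holds the error near 5% within an outcome. The documents do not support calling it a defect:

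- The argument needs a rule that pairs are tested only after a significant three-group test. The term post-hoc suggests this but the plan does not state it. Without that gate, unadjusted pairs ran at 10.5% to 12.6% in simulation with all groups equal, and a correction would be needed.
- The sentence follows the one on within-group comparisons over time, so it may also cover pairs of time points.
- The correction is valid and conservative. It costs some power, but how much depends on event rates that the document does not give.
- Analyses are reported as done. Loosening a stated correction now would itself be a choice made after the data existed.

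**What to change.** 1. State one primary outcome and cite the record that fixed it before the data were seen, such as the protocol approved by the ethics committee on 30 March 2022. Test it at two-sided 0.05.
2. List the remaining wound outcomes, closing the open lists, and say whether the clinical signs are analysed as one infection outcome or separately. Report these outcomes with Holm-adjusted p-values, applied to the three-group test of each, or label them exploratory.
3. If no earlier record names a primary outcome, say so, label all results exploratory, and apply Holm across the listed wound outcomes.
4. Keep the stated Bonferroni correction for pairwise comparisons. It continues to protect pairs within an outcome only.

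Cost: no new data, but more than a change of wording. Results already analysed need relabelling or adjusted p-values, and some findings with p just under 0.05 can no longer be called significant.
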